**Statistical Analysis:**

Approximately 300 patients will be randomized at a 1:1:1 ratio in the Blinded Treatment Dosing Period to ixekizumab 80 mg Q2W, ixekizumab 80 mg Q4W, and placebo. With 100 patients per treatment group, this study will have approximately 96% power to test the superiority of ixekizumab Q2W to placebo for the ASAS40 at Week 16. The following assumptions were used for the power calculations for ASAS40 response rates at Week 16 regardless of ixekizumab starting dose: 27% for ixekizumab Q2W treatment group and 7% for placebo group. A 2-sided Fisher's exact test at the 0.05 level is assumed. The efficacy analyses for the Blinded Treatment Dosing Period will be conducted on the intent-to-treat (ITT) population, and safety analyses will be conducted on the safety population.

Comparisons between each ixekizumab treatment group (80 mg Q2W or 80 mg Q4W) and placebo will be performed for all analyses in the Blinded Treatment Dosing Period. Unless otherwise specified, ixekizumab 80 mg Q2W and Q4W groups will be analyzed without regard to starting dose. The primary analysis method for treatment group comparisons of categorical efficacy and health outcomes variables will be a logistic regression analysis with treatment, geographic region, baseline CRP status (nonelevated or elevated), and prior number of TNF inhibitor used (1 or 2) as factors, using the nonresponder imputation (NRI) method. Under NRI, all nonresponders at Week

16 (Visit 8), as well as all patients who discontinue study treatment at any time prior to Week 16 for any reason, will be defined as nonresponders for the NRI analysis at Week 16. Randomized patients without any postbaseline observation will also be defined as nonresponders for the NRI analysis. A graphical multiple testing strategy for the primary and major secondary objectives will be implemented to control the family-wise type I error rate at a 2-sided  $\alpha$  level of 0.05.

The primary analyses for the continuous efficacy and health outcomes variables will be made using mixed-effects model of repeated measures (MMRM) analysis with treatment, geographic region, baseline CRP status, prior number of TNF inhibitor used, baseline value, visit, baseline value-by-visit, and treatment-by-visit as fixed factors.

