
 • To determine if the effect of either ixekizumab regimen is maintained through Week 52 • To explore effect of starting dose (160 mg compared to 80 mg) • To evaluate the incidence of anti-ixekizumab antibodies and their relationship to the efficacy of ixekizumab • To measure ixekizumab exposure and assess the relationship between exposure and efficacy, and exposure and immunogenicity 	
All endpoints assessed at Week 16 (above) and during the 16-week placebo-controlled period (above) will continue to be assessed through Week 52 (with the exception of MRI-related endpoints).
 
In addition, the following endpoint is added:
 
 • NSAID intake (ASAS-NSAID score and % of patients taking NSAIDs) • Onset of action and treatment response (ASAS and CRP) during the placebo-controlled period • Efficacy response rates listed below at Weeks 16 and 52 by treatment-emergent anti-drug antibody (TE-ADA) status and by neutralizing anti-drug antibody (NAb) status: 
 ○ Proportion of patients achieving ASAS40 ○ Proportion of patients achieving ASAS20 ○ Proportion of patients achieving ASDAS <2.1 • Serum trough concentrations of ixekizumab • Model parameters for the exposure-response relationship between ixekizumab serum trough concentrations and efficacy endpoints (for example, ASAS20, ASAS40) at Weeks 16 and/or 52 • Ixekizumab serum trough concentrations associated

Abbreviations: CRP = C-reactive protein; DNA – deoxyribonucleic acid; mRNA = messenger ribonucleic acid; NSAID = nonsteroidal anti-inflammatory drug; Q2W = every 2 weeks; Q4W = every 4 weeks; TE-ADA = treatment-emergent anti-drug antibody.

5. Study Design

[figure not shown]
This section contains the summary of study design, the method of treatment assignment, and the sample size determination from the protocol for Study I1F-MC-RHBW (RHBW).

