5.1. Summary of Study Design

Study RHBW is a Phase 3, multicenter, randomized, double-blind, placebo-controlled, parallel-group, outpatient study examining the efficacy and safety of 2 ixekizumab treatment regimens (80 mg every 2 weeks [Q2W] and 80 mg every 4 weeks [Q4W] subcutaneous [SC]), as compared to placebo SC in patients with active radiographic axial spondyloarthritis (rad-axSpA) who are tumor necrosis factor (TNF) inhibitor-experienced, during a double-blind, 16-week treatment period (Period 2). Starting doses of 80 mg and 160 mg (at Week 0) will be evaluated for each ixekizumab regimen.

Study RHBW will also evaluate long-term efficacy and safety of ixekizumab during the Extended Treatment Period (Period 3) for a total treatment duration of 1 year (52 weeks). Patients who complete Study RHBW may be eligible to enroll into a long-term study (Study I1F-MC-RHBY [RHBY]) for up to 2 additional years. Patients who do not enroll into Study RHBY will complete the Post-Treatment Follow-Up Period (Period 4) in Study RHBW.

[Figure RHBW.5.1](#) illustrates the study design.

Abbreviations: LV = last visit; LY = ixekizumab; n = number of patients; Q2W = every 2 weeks; Q4W = every 4 weeks; SC = subcutaneous; V = study visit; W = study week.

- a All patients will receive 2 injections at baseline, as detailed in Protocol Section 6.1. Patients randomized to an ixekizumab regimen will be randomized to a 160 mg starting dose or 80 mg starting dose at a 1:1 ratio (within each ixekizumab regimen).
- b All patients will receive 2 injections at Week 16, as detailed in Protocol Section 6.1. Patients randomized to placebo at Week 0 will begin ixekizumab 80 mg Q4W or ixekizumab 80 mg Q2W at Week 16 with a 160 mg starting dose (Protocol Section 6.1).
- c Patients who discontinue from study treatment for any reason and who have received at least 1 dose of investigational product will continue to the early termination visit (ETV) before entering the Post-Treatment Follow-Up Period. V801 and V802 are required for all patients; V803 may be needed depending on neutrophil counts (Protocol Section 6.1).

Figure RHBW.5.1. Illustration of study design for Clinical Protocol I1F-MC-RHBW.

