6.1.1. General Considerations for Analyses during the Blinded Treatment Dosing Period (Period 2)

Comparisons between each ixekizumab regimen (80 mg Q2W or 80 mg Q4W) and placebo will be performed for all analyses in Period 2.

Period 2 starts at the first injection of study treatment at Week 0 (Visit 2) and ends before the first injection of study treatment at Week 16 (Visit 8) or the early termination visit (ETV) (between Weeks 0 and 16).

Baseline will be defined as the last available value before the first injection for efficacy, health outcome, and safety analyses. In most cases, this will be the measure recorded at Week 0 (Visit 2). For efficacy measures, if the patient does not take any injection, the last available value on or before randomization date will be used. Change from baseline will be calculated as the visit value of interest minus the baseline value. For safety analyses using a baseline period, the baseline period is defined as the time from Visit 1 to the date/time of the first injection.

The randomization to treatment groups is stratified by country, screening CRP status (nonelevated versus elevated), and number of prior TNF inhibitors used (1 or 2) as described in Section 5.2. The countries will be categorized into geographic regions for analysis. Geographic regions are defined in Section 6.2. Unless otherwise specified, the statistical analysis models will adjust for geographic region, baseline CRP status, and number of prior TNF inhibitors used.

Unless otherwise specified, treatment groups of ixekizumab 80 mg Q2W and Q4W groups will be analyzed without regard to starting dose.

The primary analysis method for treatment comparisons of categorical efficacy and health outcomes variables at specific time points will be made using a logistic regression analysis with treatment, geographic region (Europe and non-Europe), number of prior TNF inhibitors used, and baseline CRP status in the model using PROC Logistic with a Wald test. The odds ratio and 95% CIs will be reported; treatment difference and 95% CI will also be reported. Secondary analysis will be conducted using a Fisher's exact test. In the case when the logistic regression model does not produce statistical results due to sparse data, Fisher's exact test will be used.

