For response rates, starting dose comparisons within ixekizumab Q2W or Q4W treatment regimens will be based on a logistic regression model with treatment, starting dose, and treatment-by-starting-dose interaction (only ixekizumab Q2W and Q4W will be included in the analyses). Starting dose comparison combining ixekizumab Q2W and Q4W treatment regimens will be based on a logistic regression model with only starting dose in the model.

For mean change analysis, starting dose comparisons within ixekizumab Q2W or Q4W treatment regimens will be based on a MMRM model with treatment, starting dose, baseline value, visit, baseline value-by-visit, treatment-by-visit, treatment-by-starting dose, starting dose-by-visit, and treatment-by-starting dose-by-visit interactions as fixed factors. Starting dose comparison combining ixekizumab Q2W and Q4W treatment regimens will be based on a MMRM model with starting dose, baseline value, visit, baseline value-by-visit, and starting dose-by-visit

interaction as fixed factors. The differences in response rates and LS mean changes between starting doses and the corresponding 95% CI will be reported as well.

Time-to-onset analyses will focus on earlier time points (for example, Weeks 1, 2, 4, and so on) for abovementioned response variables in a similar fashion. For time-to-first-clinical-response analysis, starting dose comparisons within and across ixekizumab Q2W and Q4W treatment regimens will be based on a log-rank test.

For variables that are not collected at each postbaseline visit, data may exist at visits where the variable was not scheduled to be collected, due to early discontinuation visits. In these situations, data from the early discontinuation visit that do not correspond to the planned collection schedule will be excluded from the MMRM and categorical MMRM analyses (Andersen and Millen 2013). However, the data will still be used in other analyses, including shift analyses, change from baseline to last-observation carried forward (LOCF) or modified baseline observation carried forward (mBOCF) endpoint analyses, and other categorical analyses.

For selective continuous efficacy variables, percent improvement will be calculated as $100 \times (\text{baseline score} - \text{observed scores}) / \text{baseline score}$, unless specified otherwise. If a patient has experienced an improvement, this measure will be positive. If a patient has experienced a worsening, this measure will be negative.

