Figure RHBW.6.3. Graphical multiple testing scheme used within the Tier 2 group of endpoints.

There will be no adjustment for multiple comparisons for any other analyses.

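### The starting-dose logistic models drop the SAP's default covariates without a stated reason (the pooled models drop regimen too), giving up a little power on an exploratory objective

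*SAP*

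**What the plan says.** SAP 6.1.1 sets a default for Period 2. Unless otherwise specified, "the statistical analysis models will adjust for geographic region, baseline CRP status, and number of prior TNF inhibitors used". SAP 6.2 repeats it.

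For starting dose, the same section specifies four models:

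- **Within-regimen logistic:** regimen, starting dose and their interaction.
- **Pooled logistic:** a "logistic regression model with only starting dose in the model".
- **Within-regimen MMRM:** regimen, starting dose, baseline value, visit and their listed interactions.
- **Pooled MMRM:** starting dose, baseline value, visit, and the interactions of visit with the other two.

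None lists region, CRP status or number of prior TNF inhibitors. The response variables named are ASAS40 and ASAS20, and CRP is the only continuous measure named (SAP 6.1.1 and 6.10.4).

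On allocation, the footnote to the design figure in SAP 5.1 states: "Patients randomized to an ixekizumab regimen will be randomized to a 160 mg starting dose or 80 mg starting dose at a 1:1 ratio". SAP 5.2 stratifies randomization by country, CRP status and number of prior TNF inhibitors. Protocol 4.3 explains the last two as reported or potential influences on response. Protocol 9.2.1 left the details of the starting-dose evaluation to the SAP.

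SAP Section 4 lists starting dose among the other secondary objectives, worded as exploration. After the graphical procedure, SAP 6.5 adds: "There will be no adjustment for multiple comparisons for any other analyses".

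**The concern.** A comparison of randomized groups that leaves out prognostic stratification factors remains valid but usually loses some efficiency. These factors were chosen as strata because they were thought to affect response, and they enter the main Period 2 efficacy models. The starting-dose comparison has little to spare, with about 100 against 100 patients pooled and 50 against 50 within a regimen. Dropping the covariates here, with no reason given, looks like an oversight. What is at stake is some power, and the calibration of the test and interval, for a stated but exploratory objective.

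**Working it through.** **1. The plan's own power figure.** The protocol synopsis states: "With 100 patients per treatment group, this study will have approximately 96% power" for Q2W against placebo. It assumes response rates of "27% for ixekizumab Q2W treatment group and 7% for placebo group", and "A 2-sided Fisher's exact test at the 0.05 level is assumed". Full enumeration of Fisher's test with 100 per arm gives 96.5%, which agrees. The documents give no power or precision figure for starting dose.

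**2. What the starting-dose comparison can show.** Take a 27% response rate. The standard error of a difference is √(2 × 0.27 × 0.73 / n).

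- Pooled, n = 100: 0.0628, so the 95% half-width is 1.96 × 0.0628 = 12.3 points. The difference detectable with 80% power is about 19 points.
- Within a regimen, n = 50: 0.0888, half-width 17.4 points, detectable difference about 27 points.

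Sample size is therefore the main limit.

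**3. Power with and without covariates.** The set-up was 4,000 simulated trials per setting, with 100 patients per regimen, 27% response on the 80 mg starting dose and a true starting-dose odds ratio of 2. CRP was split 60:40 elevated to nonelevated, and prior TNF inhibitors 60:40 for 1 to 2 (both SAP 5.2). Region was split 50:50 (assumed). Tests were Wald logistic at two-sided 0.05.

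The documents give no prognostic strengths. The assumed odds ratios for regimen, elevated CRP, two prior TNF inhibitors and region are:

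- weak: 1.0, 1.3, 0.8, 1.2
- moderate: 1.2, 2, 0.6, 1.5
- strong: 1.5, 3, 0.4, 2

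The documents do not say whether the starting-dose split is made within strata, so both cases were run.

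| Strength | Starting-dose allocation | Dose only | + regimen | + regimen and three factors | Total gain (points) |
|---|---|---|---|---|---|
| Weak | balanced in strata | 62.4% | 62.4% | 63.1% | 0.7 |
| Moderate | balanced in strata | 60.9% | 60.9% | 63.3% | 2.4 |
| Strong | balanced in strata | 53.3% | 53.4% | 58.2% | 4.9 |
| Weak | simple | 62.6% | 62.6% | 62.7% | 0.1 |
| Moderate | simple | 59.4% | 59.8% | 60.9% | 1.5 |
| Strong | simple | 52.3% | 53.1% | 57.2% | 4.9 |

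Simulation error is about √(0.6 × 0.4 / 4000) = 0.8 points per figure; differences within a row are paired and tighter.

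**4. Where the gain comes from.** In the moderate balanced case, the mean log odds ratio moves from 0.677 to 0.725 and its standard error from 0.305 to 0.317. The ratio goes from 0.677/0.305 = 2.22 to 0.725/0.317 = 2.29. The standard error rises; power improves because the covariate-conditional odds ratio lies further from 1. The empirical standard deviation of the response-rate difference, which the SAP also reports, stays at 0.064 in that case. Its largest fall is in the strong case with simple allocation, from 0.0670 to 0.0645, or 3.7%.

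**5. Type I error.** With no effect, strong factors and balanced strata, the dose-only test rejects 3.8% of the time and the adjusted test 5.2% (simulation error about 0.3 points). With simple allocation the figures are 4.4% and 4.8%. A separate run of the strong balanced case put the average unadjusted standard error of the response difference at 0.0624 against a true 0.0592, so the interval is about 5% too wide. With weak or moderate factors the conservatism is negligible.

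**6. The CRP MMRMs.** If the omitted factors explain a further 1%, 5% or 10% of variance beyond baseline value (assumed), the standard error is multiplied by √(1 − R²) = 0.995, 0.975 or 0.949. That is a fall of 0.5%, 2.5% or 5.1%.

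**The case against.** The best case for leaving the models alone has four parts.

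- **The exception is used, not breached.** The default applies unless otherwise specified, and the pooled logistic model is specified otherwise in plain terms. This stands. A reader might infer a violation of the SAP's own rule, but the text supports only an unexplained use of its exception.
- **Lean models are common in this SAP.** The efficacy subgroup model (6.13.1), the safety subgroup model (6.13.2) and the antidrug-antibody efficacy model (6.12.8.2.2) also leave out these factors. This stands too, so it would be wrong to say that the covariates appear in every other model.
- **Some of the adjustment is already there.** Both within-regimen models contain regimen, so it is tempting but incorrect to say that all the starting-dose models drop it. Both MMRMs carry baseline value, which for CRP is baseline CRP, so dichotomized CRP status would add little to them.
- **Little depends on it.** The objective is exploratory, and Table RHBW.6.5 lists the ASAS20 starting-dose analysis as descriptive. With weak factors the gain is under 1 point.

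These arguments limit the size of the point. None gives a reason for omitting the stratification factors from the logistic models, and no other section adds them.

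**Conclusion.** The point holds as a minor one. The starting-dose logistic models leave out region, CRP status and number of prior TNF inhibitors, and the two pooled models also leave out regimen, with no reason stated. For the pooled logistic comparison at an odds ratio of 2 the cost is about 0 to 5 points of power, almost none of it from regimen. There is slight conservatism when the strata are strongly prognostic and starting dose is balanced within them. Both results rest on assumed prognostic strengths.

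Two stronger readings are not supported. A reader might infer bias, but starting dose is randomized 1:1 within regimen, so nothing confounds the comparison; the adjusted and unadjusted odds ratios differ because they measure different quantities. A reader might also infer wasted precision, but for the logistic models the standard error of the log odds ratio rises with adjustment, and the spread of the response-rate difference hardly changes. The loss is in power. No primary or major secondary conclusion depends on these models.

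**What to change.** In SAP 6.1.1:

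- **Pooled logistic model:** add regimen, geographic region, baseline CRP status and number of prior TNF inhibitors.
- **Within-regimen logistic model:** add the last three.
- **CRP MMRMs:** add region and number of prior TNF inhibitors to both, and regimen to the pooled one. CRP status is optional because baseline CRP is already in the model.

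If the lean models are intended, one sentence giving the reason would be enough. In the same edit, reconcile the logistic analysis of ASAS20 in 6.1.1 with the descriptive entry in Table RHBW.6.5. The cost is SAP wording only: the covariates are already collected and derived for the main efficacy models, and sample size and the testing procedure do not change.

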6.1.2. General Considerations for Analyses during the Extended Treatment Period (Period 3)

Unless otherwise specified, Period 3 starts at the first injection of study treatment at Week 16 (Visit 8) and ends on the date of Week 52 (Visit 15) or the ETV (between Weeks 16 and 52).

For the efficacy and health outcomes analyses, baseline is defined as the last available value before the first injection in Period 2 and, in most cases, will be the value recorded at Week 0 (Visit 2).

Unless otherwise specified, for the safety analyses during Period 3, baseline is defined as the last available value before first injection of ixekizumab in Period 3. In most cases, this will be the measure recorded at Week 16 (Visit 8). For treatment-emergent adverse events (TEAEs), baseline is considered as those events that are ongoing before the first injection of the study treatment at Week 16.

The number and percentage of patients having a categorical efficacy response (for example, ASAS40) will be summarized by treatment group for all scheduled visits (nonresponder imputation [NRI]), including Week 52 (Visit 15) during Period 3.

In addition, the number and percentage of patients achieving response on ASAS20 for those patients who did not achieve it at Week 16, and the number and percentage of patients maintaining response for those who achieved response at Week 16 will be summarized by treatment group for all scheduled visits (NRI), including Week 52 (Visit 15) during Period 3. Similar summary will be provided for ASAS40.

Each continuous efficacy and health outcomes score and change from baseline (or percent improvement) will be summarized by treatment group at all scheduled visits, including Week 52 (Visit 15) using descriptive statistics (n, mean, SD, median, minimum, and maximum). Missing data will be imputed using mBOCF method (Section 6.3.2).

The categorical safety measures will be summarized with incidence rates. The mean change of the continuous safety measures will be summarized at all scheduled visits.

6.1.3. General Considerations for Analyses during Combined Blinded Treatment Dosing Period and Extended Treatment Period (Combined Periods 2 and 3)

Selective efficacy and health outcomes analyses will be performed for Combined Periods 2 and 3 for the ITT population who are randomized to ixekizumab at Week 0 (Visit 2). These analyses include the primary endpoint, all major secondary endpoints, as well as BASDAI50, ASDAS inactive disease, ASDAS clinically important improvement and major improvement.

Unless otherwise specified, Combined Periods 2 and 3 starts at the first injection of study treatment at Week 0 (Visit 2) and ends on the date of Week 52 (Visit 15) or the ETV (between Weeks 0 and 52).

For the efficacy and health outcomes analyses, baseline is defined as the last available value before the first injection in Period 2 and, in most cases, will be the value recorded at Week 0 (Visit 2). For efficacy measures, if the patient does not take any injection, the last available value on or before randomization date will be used.

The number and percentage of patients achieving a categorical response (for example, ASAS40) will be summarized by treatment group for all scheduled visits (NRI), including Week 52 (Visit 15).

Continuous measure score and change from baseline will be summarized by treatment group at all scheduled visits, including Week 52 (Visit 15) using descriptive statistics (n, mean, SD, median, minimum, and maximum). Missing data will be imputed using mBOCF method (Section 6.3.2).

Selected safety analyses will be performed for Combined Periods 2 and 3 for the Safety Population who are randomized to ixekizumab at Week 0 (Visit 2).

For the above safety analyses, baseline will be defined as the last available value before the first injection at Week 0. In most cases, this will be the measure recorded at Week 0 (Visit 2). For TEAEs, baseline is defined as the time from Visit 1 to the date/time of the first injection.

Additional categorical safety analyses will be conducted in the All Ixekizumab Exposures Safety Population (defined in Section 6.1.5), for each patient, and will include only periods in which ixekizumab is administered. Exposure-adjusted incidence rates of AEs during Week 0-52 timeframe will be provided. For these safety analyses, baseline is defined as follows:

- If ixekizumab is dispensed at Week 0, baseline will be defined as the last available value before the first injection at Week 0. In most cases, this will be the measure recorded at Week 0 (Visit 2). For TEAEs, baseline is defined as the time from Visit 1 to the date/time of the first injection.
- If placebo is dispensed at Week 0, then the baseline is the last nonmissing value up to visit (V8) that the patient receives first injection of ixekizumab.

